4.3. Sample size

Data on reported prevalence of TB in children with SAM from African settings is scarce and heterogeneous, largely depending on diagnostic strategies, case definitions as well as bias inherent to retrospective studies. Prevalence data gathered from the published literature varies from 1.6% to more than 30% in HIV-prevalent, urban tertiary health care hospitals, including Zambia [36], [37]. Hypothesizing an intermediate TB prevalence among children with SAM in participating sites of 15%, we will need a sample size of approximately 720 children, including children with either confirmed or unconfirmed TB, to develop a diagnostic algorithm or score with an expected sensitivity of 80%, an unacceptable sensitivity of 65% (minimal acceptable lower confidence interval limit), and 10% missing data on key predictors entering the model.

4.4. Provisional study schedule

- First inclusion: 04/11/2019
- Last inclusion : 31/12/2021
- Total inclusion period: 26 months
- Duration of follow-up for each participant once enrolled: 6 months
- Enrolment stop due to the Covid-19 pandemic: April 1st, 2020
- Enrolment restarting: August-October 2020
- Expected last visit of the last patient: 30/06/2022
- Overall duration of the study (from the first inclusion to the last visit): 32 months

4.5. Cost-effectiveness ancillary study

A cost-effectiveness study will be performed as part of the TB-Speed Project Output 5 ("Evaluation of cost-effectiveness of the proposed diagnostic approaches"). Cost-effectiveness and budget impact analyses will evaluate the incremental cost-effectiveness ratio (ICER) and the long-term impact of improving TB diagnostics in children with SAM, guide health authorities' decisions and support the implementation of the TB-Speed approach in resource-limited settings.

A mathematical model will be developed to project health-economic outcomes including TB cases and mortality in children with SAM. The model will be developed in collaboration with ScHARR of the University of Sheffield (UK) and the CaP-TB project (see Chapter 12.2.3).

The cost-effectiveness analysis will be from the health payer perspective and only direct health care costs will be included. A budget impact analysis will be conducted to evaluate the actual impact of implementing the TB-Speed approach on healthcare budgets at 2- and 5-year horizons in the countries participating in TB-Speed.

A separate analysis plan will be written for the cost-effectiveness analysis. Data collection methods for cost data are outlined in Chapter 10.1.2.

5. STUDY ENROLLMENT

5.1. Study population

5.1.1. Inclusion criteria

- Children aged 2 to 59 months
- Severe acute malnutrition defined as weight-for-height Z score (WHZ) < -3 standard deviation (SD) or mid-upper arm circumference (MUAC) < 115 mm (in children over 6 months) or clinical signs of bilateral pitting oedema [2]
- Hospitalized per hospital clinician's decision*
- Parent/guardian informed consent

*Usual criteria for hospitalisation of children with SAM recommended by WHO include: medical complications including sepsis and dehydration, severe oedema, poor appetite, and presentation of one or more Integrated Management of Childhood Illness danger signs (unable to drink or breastfeed; vomiting everything; more than one or prolonged convulsions (>15 min); lethargic or unconscious; convulsing now) [53].

5.1.2. Non-inclusion criteria

> Ongoing TB treatment or history of intake of anti-TB drugs in the last 3 months

5.2. Recruitment sites

The study will be implemented at inpatient nutrition centres from three selected tertiary hospitals in Uganda and Zambia (see Table 1). Participating hospitals are University Teaching Hospitals or equivalent in terms of level of care, located in the country capital city or major city. They are also implementing sites for the TB-Speed Pneumonia and TB-Speed HIV studies.

Table 3 shows indicative recruitment capacities of participating hospitals, based on a capacity assessment questionnaire including the number of children admitted annually for SAM. It should be noted the high prevalence of HIV infection among these children.

Country	Hospitals, City	No. children admitted for SAM (year)	Proportion of HIV infected
Uganda	Mulago National Referral Hospital, Kampala	1,200* (2016)	30%
Zambia	University Teaching Hospital, Lusaka	2,000* (2016)	50%
	Arthur Davidson Children's Hospital, Ndola	541 (2017)	

Table 3: Implementing sites and number of admissions for severe malnutrition

* Approximate number

6. STUDY INTERVENTIONS

6.1. Description of the diagnostic strategy

The diagnostic strategy will include:

- Assessment of household TB contact history
- Medical history and duration of symptoms in the previous 4 weeks
- Physical examination including vital signs
- Clinical, anthropometric and biochemical assessment of malnutrition
- Clinical assessment for other non-dietary causes of malnutrition, including

identification of important comorbidities like HIV

- A digitalized CXR (standard anteroposterior and lateral view) performed and interpreted using standardised approach
- Ultra performed on NPA and stool samples, as well as on the first of the two GAs collected
- Mycobacterial culture performed on two GAs
- Abdominal ultrasonography to assess the presence of intra-abdominal lymphadenopathies or ascites
- MLR
- QFT
- CRP

TB diagnosis will be made according to national TB guidelines (i.e. clinician's diagnosis).

6.2. Capacity building

Implementation of the TB-Speed SAM study will include a preparation and capacity building phase conducted at participating hospitals, which are tertiary level reference university teaching hospitals also involved in the TB-Speed Pneumonia and HIV studies in Zambia and Uganda. Sites which are not already equipped will be provided with digital radiography (DR) plates for digital CXR, ultrasound machine, sample collection material (including battery-operated suction machines for NPA collection) and IGRA kits. Laboratories will be equipped with GeneXpert devices if not available through National Programs as well as -80°C freezers for biobanking.

Specific training will be provided to site investigators and hospital staff in nutrition wards (doctors and nurses) on TB diagnosis, study procedures, and Good Clinical Practice (GCP). Initial training will be provided onsite by the study central coordinating team. Based on didactic and practical presentation, trainings will include the following topics:

[figure not shown]
- Childhood TB diagnosis and management
- Clinical follow-up (eligibility criteria, informed consent process, patient schedule, TB assessment, management in the case of AE/SAEs)
- Biological samples collection (NPA) and laboratory procedures including biobanking
- Non-routine TB assessment procedures and their interpretation (QuantiFERON®-TB Gold, MLR, CRP, abdominal echography)
- Data collection and use of electronic CRF
- Data management and monitoring
- Use of DR plates

At the end of the study, site clinicians will be trained on the use of the developed algorithm and related interpretation of the different diagnostic tests.

6.3. Implementation at site level

The TB-Speed SAM study will be implemented in 3 tertiary healthcare level hospitals in Uganda and Zambia (see Table 1 and Table 3). A total of 720 children <5 years old with WHO-defined severe acute malnutrition will be enrolled, that is approximately 240 participants per hospital, with a competitive recruitment. The inclusion period will last until the expected number of children enrolled is reached, which could be achieved in about 32 months based on hospital admission numbers (see Chapter 5.2) and the overall delay incurred by the study, in particular due to the Covid-19 pandemic.

6.4. Study flow chart

7. STUDY PROCEDURES

7.1. Selection process

Any child younger than 5 years old, hospitalized and presenting with SAM at inpatient nutrition centres of selected hospitals, will be consecutively screened for eligibility by study nurses and offered to participate to the study.

Assessment for eligibility will be detailed in specific clinical SOPs.

7.2. Obtaining informed consent

The consent process will be conducted only once the child is stabilized, i.e. by 24 to 48 hours following admission. In any case, the clinical management of the child will be prioritized over research.

Parent(s)/guardian(s) of eligible children will be explained the purpose, the nature of constraints and the foreseeable risks and benefits of the study. Parent(s)/guardian(s) will be informed that participation is voluntary and that they will be free, without justification, to withdraw from the study at any moment without consequence on the quality of care and follow-up provided to their child. In addition to oral explanations, a written information sheet will be systematically provided (see Appendix 6). Documents with pictures will be available to help the parents to better understand the exams proposed in the study.

The informed consent process will be implemented by the study nurses. They will ensure that parent(s)/guardian(s) have read and understood the content of the information sheet, and that they have received answers to all their questions before signing the informed consent. If one of the parent(s)/guardian(s) does not agree on the child's participation, the child will not be enrolled. If the participation agreement is given by the parent(s)/guardian(s), the consent form will be completed, signed and dated by the parent(s)/guardian(s) and the study nurses and/or site clinicians/investigators. Oral consent in the presence of a literate witness (not from the medical team) is acceptable in the case of illiteracy. The consent form will include separate consent for frozen samples conservation.

A copy of the signed consent will be given to parent(s)/guardian(s). The original consent form will be retained by the site Principal Investigator (PI) in a safe place inaccessible to others, even when moving, throughout the study period and for 15 years after its end.

In the absence of national regulation, will be considered as a guardian a person who usually assumes responsibility for the child's custody, care, and maintenance even though no court order exists formally appointing the person as the guardian, custodian, or adoptive parent of the child. Should any of the child's parents be alive but not living with the child, the usual caregiver will be considered as a guardian.

7.3. Patient schedule

Table 4: Patient schedule including specimen collection in children

	Study visits						
	Inclusion (D0)	D3 (+/-2 days)	D15 (+/-2 days)	Month 1	Month 2 (+/-7	Month 3 days)	Month 6
Eligibility criteria	Х	uuyo/	uuyo/		(., ,		
Informed consent	X						
Clinical evaluation ¹	X	Х	Х	x	Х	Х	х
Medical and treatment history	X		X	X	X	X	X
Initial TB assessment	X						
Chest X-Ray	X(○) ²	Result			Х		х
Abdominal ultrasound	X	Result					
Lab assessment:		rtoodit					
- HIV diagnosis ³	0	Result					
- Malaria test	X(○) ⁴	rtooun					
- Complete Blood Count (CBC)	X(○) ⁵	Result		х			
- Transaminases + CRP	Х	Results		Х			
- QFT	Х	Result		(X) ⁶			
Maximal number of tubes collected ^{6,7}	10 (9)			6 (2)			
Maximal volume of blood collected ^{6,7,8}	13 mL (12.5 mL)			4 mL (6 mL)			
NPA	Х			(X)	(X)		
Stool sample	Х	(X)		(X)	(X)		
2 GAs		X(○)²		(X)	(X)		
Xpert MTB/RIF Ultra	Х	Result		(X)	(X)		
Mycobacterial culture (on 2 GAs)		Х		(X)	(X)		
Safety/feasibility/tolerability/ acceptability assessment	Х						
 Biobank (frozen samples): Plasma Whole blood NPA, stool, GA leftovers Urine 	(X) ⁶ X X X						
TB treatment if needed ⁹		0	0	0	0	0	0
TB drug adherence assessment			0	0	0	0	0
Treatment of SAM ⁹	0	0	0	0	0	0	
Treatment and care of co-morbidities if needed ⁹ (HIV infection, other)	0	0	0	0	0	0	0
Nutritional status assessment	0	0	0	0	0	0	0
TB treatment response				1			0

 \circ Routine care

X Research

(1) Content of clinical evaluation varies with the visit

(2) Performed as part of routine care in case of TB suspicion

(3) Performed if not available in the patient medical chart

(4) Possibly performed as part of routine care in case of clinical suspicion of malaria

(5) Possibly performed as part of routine care for anaemia assessment

(6) In children <18 months weighing <5 kg, or children presenting with signs of severe anaemia (conjunctival or palmar pallor): QFT test will be performed at M1 and plasma sample for biobank will not be

collected, except in children with signs of severe anaemia if they will benefit from blood transfusion; QFT test will be preferably done just before transfusion. Plasma sample for biobank will not be collected

- (7) In children >18 months: 2 mL of whole blood collected on plain tube for HIV serology; 3 x 2 mL collected on EDTA tube for CBC, malaria test and plasma biobank; 2 mL collected on heparin tube for transaminases and CRP; 4 x 1 mL collected on QFT tubes; 2.5 mL collected on Paxgene Blood RNA tube for biobank. In children <18 months: HIV testing will be performed by PCR on 500 μL (maximum) dried blood spot.

- (8) Volume of blood draw must not exceed 3 ml/kg/visit and 7 ml/kg/6 weeks.
- (9) According to national treatment guidelines based on WHO recommendations

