11.8. Laboratory evaluations

• Biological samples collection

Procedures for sample collection, transportation, and processing at the laboratory will be detailed in specific SOPs. To minimize the risk for participants, collection of naso/oropharyngeal swabs for SARS-CoV-2 detection will be performed either by the study nurses collecting NPA, who will receive specific training, or by specialized staff from the Covid surveillance team according to country policy.

Sample type	Minimal amount required	Laboratory test	D0- D3	M6	D15- M6
1 st naso/oropharyngeal swab ^a	minor (swabbing of the nasal/pharyngeal mucosa surface)	SARS-CoV-2 RT-PCR	х		
Stool sample ^b	1 g	SARS-CoV-2 RT-PCR	Х		
2 nd naso/oropharyngeal swab ^c	minor (swabbing of the nasal/pharyngeal mucosa surface)	SARS-CoV-2 RT-PCR			х
Blood (EDTA or dry tube) ^d	2 mL ^d	Sickle cell disease	Х		
DBS	approximately 50 µL (0.05 mL) collected by finger/heel/toe prick	SARS-CoV-2 serology	Х	х	

^a For young infants (< 6 months) an oropharyngeal swab is preferred due to the small diameter of nasal passage and increased risk of trauma.

^b If the volume of the stool sample collected for the TB-Speed SAM study does not allow for 1) Ultra testing, 2) biobanking, and 3) SARS-CoV-2 testing, an additional stool sample will be collected.

^c The 2nd swab will be collected in children negative for SARS-CoV-2 at inclusion showing new symptoms suggestive of Covid during follow-up.

^d Possibly performed on the same tube than CBC for the SAM study to avoid additional sampling. Volume of blood draw must not exceed 3 ml/kg/visit and 7ml/kg/6 weeks.

The swabs will be referred for immediate testing whenever possible. However, depending on laboratory testing capacities and national policies, it may be possible only for children fitting indication of Covid-19 testing (i.e. meeting suspect case definition, see Appendix 6). If the testing delay is above 72h, the swabs will be stored at -80°C until further testing. The stool sample and the DBS will be stored at the country Central Laboratory to be tested later on.

• RT-PCR for SARS-Cov-2

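### For children over 18 months, the tubes itemised in Table 4 note 7 sum to 16.5 mL, but the row the note annotates gives a maximum of 12.5 mL and Table 5b calls the same 12.5 mL a minimum

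*Protocol*

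**What the plan says.** Table 4 (Protocol 7.3) has a row for the maximal volume of blood collected. At inclusion it reads 13 mL, with 12.5 mL in brackets, and it refers to notes 6, 7 and 8. The row above it gives 10 (9) tubes.

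For children over 18 months, note 7 lists "2 mL of whole blood collected on plain tube for HIV serology; 3 x 2 mL collected on EDTA tube" (the EDTA tubes serve blood count, malaria test and plasma biobank), then "2 mL collected on heparin tube for transaminases and CRP", then "4 x 1 mL collected on QFT tubes; 2.5 mL collected on Paxgene Blood RNA tube for biobank". Note 8 sets the limits: 3 mL/kg per visit and 7 mL/kg over 6 weeks.

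Table 5b (Protocol 8.1) covers the same age group and visit. It shows HIV serology as a 50 µL prick and QFT as 2 mL, and totals 12.5 mL in 9 tubes (10.5 mL if malaria test and blood count share a tube). It calls that total the minimal volume required.

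Section 11.8 adds a 2 mL blood sample for sickle cell disease at D0-D3 for sub-study participants. Its note d says "Possibly performed on the same tube than CBC for the SAM study to avoid additional sampling".

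Note 6 reduces sampling in children under 18 months who weigh less than 5 kg, and in children with signs of severe anaemia.

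**The concern.** A figure labelled as a maximum should be at least as large as the list given in support of it. Here the note explaining the maximum lists about a third more blood than the row allows, and a second table presents the same number as a floor. A site can follow note 7 or Table 5b in good faith and draw different amounts.

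The participants are severely malnourished children, and the protocol itself plans for severe anaemia among them. Per-visit volume is a burden figure that ethics committees rely on, and the weight-based limit is the protection in the lightest children. The primary analysis is not affected.

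**Working it through.** **Step 1. Reproduce the stated totals from Tables 5a and 5b (mL).**

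- Table 5b, over 18 months: HIV prick 0.05 + malaria 2 + blood count 2 + transaminases/CRP 2 + QFT 2 + plasma 2 + PAXgene 2.5 = 12.55, stated as 12.5. With malaria test and blood count in one tube: 10.55, stated as 10.5. Tubes, not counting the prick: 1 + 1 + 1 + 4 + 1 + 1 = 9. All reproduce.
- Table 5a, under 18 months and over 5 kg: HIV PCR 0.5 + 2 + 2 + 2 + 2 + 2 + 2.5 = 13.0, and 11.0 with the shared tube. Both reproduce.

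**Step 2. Sum note 7 for children over 18 months.**

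| Item | Note 7 (mL) | Table 5b (mL) | Difference |
|---|---|---|---|
| HIV serology | 2 | 0.05 | 1.95 |
| Blood count, malaria test, plasma | 3 × 2 = 6 | 6 | 0 |
| Transaminases and CRP | 2 | 2 | 0 |
| QFT | 4 × 1 = 4 | 2 | 2 |
| PAXgene | 2.5 | 2.5 | 0 |
| **Total** | **16.5** | **12.55** | **3.95** |

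Tubes in note 7: 1 + 3 + 1 + 4 + 1 = 10. Against the stated 12.5 mL the excess is 16.5 − 12.5 = 4 mL, and 4 / 12.5 = 32%. With a shared malaria/blood count tube, note 7 gives 14.5 mL, still above 12.5 mL.

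Table 4 does not define its bracket. I read 12.5 mL as the figure for children over 18 months because it matches Table 5b. The contradiction does not depend on that: 16.5 mL also exceeds the unbracketed 13 mL.

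**Step 3. Add the sub-study sample.** In a separate tube: 16.5 + 2 = 18.5 mL (the dried blood spot, about 0.05 mL, is ignored). If it shares the blood count tube, the total stays at 16.5 mL. The range is therefore 16.5 to 18.5 mL, or 14.5 mL if malaria test, blood count and sickle cell test all share one tube.

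**Step 4. Compare with the protocol's limits.** Lowest weight compatible with 3 mL/kg/visit = volume / 3. For 7 mL/kg over 6 weeks, add the 4 mL Month 1 draw: (volume + 4) / 7.

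| D0 volume (mL) | Per-visit limit exceeded below (kg) | 6-week limit exceeded below (kg) |
|---|---|---|
| 12.5 | 4.17 | 2.36 |
| 14.5 | 4.83 | 2.64 |
| 16.5 | 5.50 | 2.93 |
| 18.5 | 6.17 | 3.21 |

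The per-visit limit is the one that matters. The weight-based part of note 6 applies only under 18 months, so for a light, non-anaemic older child no table names a reduced set.

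**Step 5. Lesser points.**

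- Table 5a, under 5 kg or anaemia: 13 − 2 (QFT) − 2 (plasma) = 9.0 mL against a stated 8.5 mL (7.0 against 6.5 with the shared tube). The 0.5 mL equals the HIV sample, which is taken only if status is not in the chart. This table is broken in the available text, so the point carries little weight.
- The severe-anaemia clause of note 6 has no age limit, yet Table 5b shows QFT and biobank plasma at D0 without repeating that exception.

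**The case against.** The best defence is that Tables 5a (over 5 kg) and 5b are the working tables and they add up, so the fault lies in one note. That stands: it would be wrong to infer that the protocol's blood totals fail to sum in general. It does not remove the contradiction between note 7 and the row that cites it, nor the opposite labels on 12.5 mL.

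A second defence is that note 7 can be brought down to 12.5 mL if HIV status is already in the chart (−2) and malaria test and blood count share a tube (−2). True, but that is a favourable case; a maximum has to cover the child who needs every item.

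Three stronger readings are tempting, and the documents do not support them:

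- **That the protocol allows draws above 3 mL/kg.** The limit is a binding rule, repeated in the notes to several tables, and section 8.1 says that an SOP will rank tests when too little blood is obtained, with clinical tests ahead of biobank. The likely result in a very light child is an incomplete set. No weights are given for children over 18 months, so how many could be affected, if any, is unknown.
- **That 18.5 mL is the expected draw.** It requires sub-study participation, undocumented sickle cell and HIV status, and no tube sharing, which the protocol allows or encourages.
- **That younger children face the same excess.** Note 7 states 4 × 1 mL for QFT only for children over 18 months; carrying it over to younger children is not warranted.

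Nor can one say that the totals submitted to ethics committees are wrong. Note 7 may be the item in error, and the consent material is not available to check.

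**Conclusion.** The contradiction holds for children over 18 months: 16.5 mL in 10 tubes by note 7, against 12.5 mL labelled maximal in Table 4 and minimal in Table 5b. The 4 mL gap (+32%) is fully explained by the HIV and QFT volumes. This part rests only on addition, plus the reading of the Table 4 bracket, without which the conflict would still exist against 13 mL. The omission of a separate sickle cell tube from every stated maximum also holds, with 18.5 mL as an upper bound.

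The conflict with 3 mL/kg/visit is conditional on a child over 18 months weighing under 5.5 kg on the note 7 set (4.2 kg at 12.5 mL, 6.2 kg at 18.5 mL). The Table 5a difference and the unrepeated anaemia exception are minor. This should be corrected because it concerns a safety figure and is easily put right; it does not bear on the trial's statistical conclusions.

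**What to change.** Reconcile Table 4 with its notes 6 to 8, Tables 5a and 5b, and section 11.8. For each age, weight and anaemia stratum, give one itemised list, including the sub-study tube with and without sharing. Its sum should equal the stated total, be labelled maximal or minimal in the same way throughout, and be shown against the 3 mL/kg/visit and 7 mL/kg/6-week limits. State what the brackets in Table 4 mean, and whether the anaemia exception applies over 18 months.

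The sponsor's clinical team must decide which volumes and exceptions apply; this review takes no position on that. If the reconciled maximum differs from the one submitted, notify the ethics committees. The cost is a correction to the protocol tables and, if needed, that notification. Sample size and analysis are unchanged.

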7.4. Inclusion visit

After obtaining informed consent, the following procedures will be performed during the inclusion visit:

• Complete clinical evaluation

The following data will be abstracted form existing file; additional data will be collected by site investigators or study nurses

- Reason for hospitalization
- Demographic information (sex, month and year of birth)
- Physical examination including vital signs (respiratory rate, heart rate, temperature, measurement of oxygen saturation), severe dehydration, features of shock
- Clinical and anthropometric assessment of malnutrition: WHZ, MUAC, presence and severity of oedema, medical complications², danger signs³, anaemia
- Clinical assessment for other non-dietary causes of malnutrition, including identification of important comorbidities like HIV infection, intestinal infections, malaria
- Interview of parent/guardian on medical history, past and current medication and immunization (including BCG)
- HIV status (if unknown) and history of antiretroviral therapy (ART)
- TB assessment: family exposure, history and duration of symptoms in the previous 4 weeks, including cough, signs of pneumonia, fever, diarrhoea, neurological signs
- Medical imaging
 - A digitalized CXR (standard anteroposterior and lateral view) will be realized and interpreted using standardised approach
 - Abdominal ultrasonography will be systematically performed to assess the presence of intra-abdominal lymphadenopathies, splenic micro-abscesses, hepatic abscesses or ascites

Medical imaging will be performed as soon as possible and within 24 hours of inclusion to enable quick TB diagnosis. In very sick children, CXR and abdominal ultrasonography could be postponed by 2 to 3 days.

- **Blood samples** (see section 8.2.5)
 - For HIV testing (in children with unknown HIV status, using national guidelines)
 - For malaria testing (rapid test and/or thick smear)
 - For complete blood count (anaemia assessment), transaminases, and CRP
 - For the QFT assay
 - For biobanking (storage of frozen samples)
- **Bacteriological specimen collection** (see section 8.1)

Initial bacteriological specimen collection will be done as soon as possible and within 24 hours to 48 hours of stabilization by trained nurses, including:

² hypoglycemia, hypothermia, dehydration, sepsis, lethargy; skin, respiratory or urinary tract infections [53].

³ unable to drink or breastfeed; vomits everything; has had convulsions (more than one or prolonged >15 min); lethargic or unconscious; convulsing now [53].

- 1 NPA, collected by the nurse on the day of admission without prior nasal instillation (see Appendix 3);
- 1 stool sample, collected as soon as the child is able to produce stool (see Appendix 4);
- 2 GAs.

NPA and GAs will be done under SpO2 monitoring. They will not be attempted in children presenting severe respiratory distress or SpO2 <90% under appropriate oxygen therapy, severe dehydration or features of shock. Advice will be sought from a clinician not directly involved in the study to make the determination on a case by case basis for very sick children.

The safety of bacteriological specimen collection (NPA and GA) will be assessed by study nurses. Contraindications, implementation of sample collection procedures, and safety monitoring during collection will be detailed in study procedures.

The feasibility and tolerability of NPA will be assessed using qualitative and quantitative tools (Cf Chapter 7.6) in a sub-group of children.

Bacteriological tests performed on collected specimen are detailed in Chapter 8.2.

Additionally, a urine sample will be collected for biobanking.

Extra tests not planned by the protocol will be requested by the clinician in accordance with his/her practice and the national recommendations.

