9.3. Reporting of adverse events

AEs occurring as a consequence of NPA collection, primary and secondary diagnosis of illness causing initial hospitalisation, death and cause of death, primary and secondary diagnosis of illness causing any hospital readmission will be reported in the CRF.

There will be no systematic reporting of other AEs in the study.

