9.4. Notification of serious adverse events

In this diagnostic study without investigational medicinal product, and with very low expected risk of AEs linked to the intervention, there will be no systematic notification of SAEs to the sponsor at the exception of:

- Death;
- Life-threatening AEs, excluding asymptomatic biological AEs of grade 4
- SAEs related to NPA collection.

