9.5. Responsibilities of the investigators

The investigators are responsible for:

- Grading the severity of AEs occurring from NPA collection reported by study nurses as severe or potentially life-threatening.
- Reporting SAEs, as defined above, to the sponsor and to the appropriate country authorities, according to the procedures described in section 9.4.
- Assessing the causality of all SAE in relation to the study intervention and to concomitant intervention/medication.

The assessment on expectedness will be done by the sponsor.

SAEs, as defined above, should be reported as soon as they are known to the country CTU according to the last updated SOPs. A specific "SAE report form" will be used. SAEs will be reported immediately by the country CTU to the Inserm Pharmacovigilance Department according to appropriate SOPs. If needed, queries on SAEs will be sent to the investigators by the Inserm Pharmacovigilance Department representative.

All SAE must be reported if it occurs in a participant:

- from the date of signature of the informed consent to the study;
- during the follow-up of the participant scheduled by the study;
- until 4 weeks after the end of follow-up when it is related to the study intervention.

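### Protocol section 7.4 puts the baseline research NPA on the admission day, which cannot be squared with sections 7.2 and 7.4 and Table 4 for any child consented on a later date

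*Protocol*

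**What the plan says.** Five places in the protocol bear on when the baseline NPA is taken and when its harms start to count.

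- **Section 7.2:** "The consent process will be conducted only once the child is stabilized, i.e. by 24 to 48 hours following admission".
- **Section 7.4, opening sentence:** "After obtaining informed consent, the following procedures will be performed during the inclusion visit". The NPA is one of the procedures that follow.
- **Section 7.4, lead-in to the specimen list:** "Initial bacteriological specimen collection will be done as soon as possible and within 24 hours to 48 hours of stabilization by trained nurses".
- **Section 7.4, NPA bullet under that lead-in:** "1 NPA, collected by the nurse on the day of admission without prior nasal instillation".
- **Table 4 (section 7.3):** the NPA stands in the inclusion (D0) column, coded as research only. The chest X-ray and gastric aspirates in the same table also carry the routine-care symbol, for cases of TB suspicion.

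On safety, section 9.3 has "AEs occurring as a consequence of NPA collection" entered in the CRF, and section 9.4 makes "SAEs related to NPA collection" notifiable to the sponsor. Section 9.5 counts SAEs "from the date of signature of the informed consent to the study". NPA safety is secondary endpoint 7 in section 3.2.

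**The concern.** The NPA bullet is the most specific instruction in the list and the one a nurse would read at the bedside. It counts from admission. The other statements count from consent, stabilisation or inclusion. These are different moments in any child who is not stabilised and consented on the day of arrival.

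Two things are at stake. The first is consent: because Table 4 codes the baseline NPA as research only, an aspirate taken before consent could not be explained as routine care. The second is safety capture: the protocol intends to collect and notify harms of NPA collection, but its SAE window opens only at consent signature. Section 9.2 lists expected collection events for the NPA and for no other specimen, and they include rare low oxygen saturation and slowing of the heart rate.

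**Working it through.** No sample size, power or event rate enters this point. The check places the passages on one clock, with admission as hour 0.

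**Constraints**

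1. Bullet (7.4): NPA date = admission date.
2. Section 7.2: consent only after stabilisation, by 24 to 48 h.
3. Opening sentence of 7.4: NPA after consent.
4. Specimen lead-in (7.4): NPA within 24 to 48 h of stabilisation.
5. Table 4: NPA at inclusion (D0).
6. Section 9.5: SAE window opens on the date of consent signature.

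**Case A: stabilised and consented on the admission date.** Section 7.2 says by 24 to 48 hours, which can be read as an outer limit and not as a minimum wait. Consent and then NPA on that same date satisfy constraints 1 to 5. Constraint 6 is also satisfied, because the window opens on the date of signature. There is no conflict.

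**Case B: consented 24 to 48 h after admission.** The consent date is 1 or 2 calendar days after the admission date. An NPA on the admission date precedes consent by more than 0 h and up to 48 h. Constraints 1 and 3 cannot both hold. Because consent waits for stabilisation, a child who is still unstable on the admission date would also have the NPA before stabilisation, against constraint 4.

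**Case C: consented before 24 h but after midnight.** The consent date is still later than the admission date, so constraints 1 and 3 conflict here too. What matters is the change of date, not the number of hours.

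**Consequence in cases B and C, by which line is followed**

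| Line followed | NPA relative to consent | NPA relative to 9.5 window | Line breached |
|---|---|---|---|
| Opening sentence of 7.4 and Table 4 | after | inside | the bullet |
| The bullet | before | before it opens | 7.4 opening sentence, Table 4; the 7.4 stabilisation lead-in if not yet stable |

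**Would sections 9.3 and 9.4 close the gap in the second row?** Only in part. They require NPA-related events to be recorded and serious ones notified, and section 9.3 gives no start date. But section 9.1 defines an adverse event as occurring in someone participating in the research, section 10.1.1 starts individual data collection at enrolment, and section 9.5 sets an explicit start for SAEs. For an event during an NPA taken before consent, these provisions point in different directions.

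**The case against.** The strongest reply is that section 7.4 must be read as a whole. The bullet is a sub-item beneath a sentence that puts consent first and another that ties collection to stabilisation, and Table 4 agrees with both. On that reading the admission-day phrase is a slip, no NPA is ordered before consent, and every NPA lies inside the SAE window. Site monitoring also covers informed consent and the patient schedule (section 17.2.2). This reply stands as far as it goes: the consequence is conditional on the bullet being followed over its own lead-in. It does not remove the conflict, because in a child consented on a later date staff must still depart from one line or the other.

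A reader might infer several stronger things that the documents do not support:

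- **That the protocol requires NPA before consent, in essentially all of the 720 children.** Section 7.2 permits consent on the admission date, the governing sentence of 7.4 puts consent first, and no distribution of consent times is given.
- **That endpoint 7 is biased in a favourable direction.** This would need research NPAs in children who are then never enrolled. No passage provides for that, and no event rate is given.
- **That the NPA is the riskiest study procedure.** The protocol ranks none. Gastric aspiration has the same contraindications and oxygen monitoring (section 7.4), and section 16.1.1 names NPA and blood draw together and does not expect NPA to raise the risk of hypoxaemia.
- **That the sickest children would be aspirated unprotected.** Section 7.4 sets contraindications and asks for advice from a clinician not directly involved in the study for very sick children. Section 7.8.1 interrupts the procedure at acute desaturation.

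**Conclusion.** The contradiction is real and limited. It affects every child whose consent is dated after admission and no child consented on the admission date. In an affected child who had the NPA as the bullet says, a research procedure would precede consent by up to 48 hours on the section 7.2 limits. It would also precede the SAE window, and could precede stabilisation. How many children are affected, and which line sites followed, cannot be told from the protocol.

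The conclusion rests on two readings: that the admission day means the calendar date of hospital admission, and that Table 4's coding of the baseline NPA as research only is intended. It remains worth correcting because it is an operative instruction in acutely ill young children that touches consent and safety reporting.

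**What to change.** The sponsor should reconcile section 7.2, both lead-ins and the NPA bullet of section 7.4, Table 4 and section 9.5 into one statement of when the baseline NPA is taken. That statement should agree with the protocol's own rule that the section 7.4 procedures follow informed consent, so that every study NPA lies inside the SAE reporting window. Which clinical timing to adopt within that rule is for the sponsor, and none is proposed here.

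The edit is a line or so of text and adds no procedure. The cost is administrative: section 19 sends any change to the protocol through a written amendment with ethics approval.
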